Aim 2 analyses will address the dimensions of Reach, Effectiveness, Adoption, and Implementation from our conceptual framework. For Effectiveness, we will be testing for equivalence between study arms in uptake of genetic testing. We will check randomization by comparing demographic characteristics between patients in the two arms. Any characteristic(s) that are significantly different will be controlled for in the multivariable analysis. We will examine descriptive statistics, and will use Fisher's Exact test with a two-sided 0.05 significance level for univariate comparison of proportions to examine the association between study arm and uptake of genetic testing. We will next build multilevel multivariable logistic regression models to examine the effect of study arm on the outcome controlling for clinic-level (clinic type, patient volume, patient composition, number of providers), provider-level (specialty, years in practice, gender), and patient-level (e.g., sociodemographic, clinical) variables. We will examine the intra-class correlation (ICC) by clinic and provider. If a significant ICC is observed, the regression models will be extended to include random effects for clinic or provider, and fit using software for generalized mixed models. Covariates will be included in models if significant in unadjusted analyses. For Reach, using the multivariable regression models with interaction terms, we will examine whether the effects of study arm on uptake of genetic testing is modified by race/ethnicity or rurality. For Adoption, we will examine the proportions of providers and patients who access educational resources and with referrals, and whether this differs by population subgroup. For Implementation, we will assess responses to patient portal messages and completion of study workflows. Statistical significance will be assessed as $p < 0.05$; SAS 9.4 and/or Stata 15.1 will be used for analysis.

Aim 2 Sample Size

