Sample size for Aim 2 was calculated using PASS 15 based on an equivalence test for the difference of two proportions in a cluster-randomized design. Sample sizes of 480 in the patient-directed arm and 480 in enhanced standard of care arm, which were obtained by sampling 32 clusters (clinics) with 15 participants each and 16 clusters (clinics) with 30 participants each, respectively, achieve 80% power to detect equivalence. The margin of equivalence, given in terms of the difference between proportions, extends from -0.10 to 0.10. The calculations assume Likelihood Score Tests (Farrington & Manning) were used with an ICC of 0.05, and a significance level of 0.05. We believe that this is likely an overestimate of ICC based on our prior work. This sample size is sufficient for a multilevel multivariable regression analysis and achieves >95% power to detect a small effect size (0.02) attributable to 1 independent variable using an F-Test with an alpha of 0.05, adjusted for an additional 20 independent variables. To examine effect modification, sample size is calculated based on logistic regression of a binary response variable (Y) on a binary independent variable (X) and a binary confounder variable (Z). A sample size of 1,710 observations achieves 80% power at a 0.05 significance level to detect the X-Z interaction odds ratio of 1.5, using a two-sided Wald test. We will therefore enroll 1,920 patients in the Aim 2 trial to allow for about 10% attrition.

Aim 3 Analysis

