Aim 3 analysis will follow analytic procedures to address the dimension of Effectiveness from our conceptual framework. For comprehension, concordance between patient responses and information from genetic counselors' notes will be scored. We will test bivariate relationships between the outcome variables and study arm using Student's t-test or the nonparametric Wilcoxon rank-sum test between continuous variables, and chi-square test (or Fisher's exact test if small cell counts) for categorical data. We will examine distributions for continuous outcomes and transform the data if skewed. Procedures for building multilevel multivariable linear (continuous outcomes) or logistic (binary outcomes) regression models are described above. Regression models extended to include random effects for clinic or provider will be fit using software for linear mixed models for continuous outcomes and generalized linear mixed models for categorical outcomes. As with Aim 2, we will examine effect modification by testing for significant interactions between variables in regression models.

Aim 3 Sample Size

We estimate a sample size of 1,100 for a multilevel multivariable regression analysis with >90% power to detect a small effect size (0.02) attributable to 2 independent variables using an F-Test with an alpha of 0.05 using PASS 15 Software. The variables tested are adjusted for an additional 20 independent variables. To examine effect modification sample size is calculated based on logistic regression of a binary response variable (Y) on a binary independent variable (X) and a binary confounder variable (Z) with a sample size of 1,710 observations achieves 80% power at a 0.05 significance level to detect the X-Z interaction odds ratio of 1.5. Calculations assume that a two-sided Wald test is used.

IRB_00123563

Created: 6/5/2019 3:01
PM

IRB_00123563

- Request for Waiver of Consent

PI: [name]

Submitted: 3/5/2019

Title: Broadening the Reach, Impact, and
Delivery of Genetic Services**Request for Waiver or Alteration of Consent***** Requested Waivers**

Date Created	Type of Request	Purpose of Waiver Request
View 3/18/2019	Waiver of Informed Consent	Waiver of consent for chart review without patient contact

IRB_00123563

Created: 6/5/2019 3:01 PM

PI: [name]

Submitted: 3/5/2019

IRB_00123563

IRB Smart Form

Title: Broadening the Reach, Impact, and Delivery of Genetic Services

Request for Waiver or Alteration of Consent

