1,920 consent cover letters sent; up to 20,000 EHR records **Number of currently approved enrollments for this study as a whole**

960**Number of currently approved enrollments for this study location**

Enrollment since the beginning of the study at this site:

236**Total number enrolled as of today♦s date at this site**

From the beginning of the study, how many non-English speakers have been enrolled?

2

Which non-English languages were used in the enrollment process since the last review?

Yes Spanish

How many Spanish fully translated long forms were 2 How many Spanish short forms were 0 used?

Mandarin

Nepali

Vietnamese

Russian

Other

From the beginning of the study, how many participants signed consent forms but did not end up participating in the study?

0

Enrollment since the last continuing review approval at this site:

278Reported enrollment during the last continuing review**-42Number enrolled since the last continuing review**

Problems and Events**Have any unanticipated problems or adverse events involving risks to participants occurred since the last IRB approval?**

Yes No

Have there been any complaints about the research since the last IRB review?

Yes No

Date: Friday, February 2, 2024 9:30:05 PM

 IRB_00115509 - CR_12/15/2023 4:09 PM**Created: 12/15/2023 4:09 PM****PI:** [name]**Submitted: 1/4/2024****Title:** Broadening the Reach, Impact, and Delivery of Genetic Services**HELP?**

1. Status

Overall, what is the enrollment status for this study?

Open to enrollment of new participants

•

IRB_00115509 - CR_12/15/2023 4:09 PM**Created: 12/15/2023 4:09 PM****PI:** [name]**Submitted: 1/4/2024****Title:** Broadening the Reach, Impact, and Delivery of Genetic Services**HELP?**

2. Progress of Study and Enrollment Information

Overall Study Enrollment Progress

Number of currently approved enrollments for this study as a whole: 1,920 consent cover letters sent; up to 20,000 EHR records**Number enrolled across all sites at last Continuing Review:** 794**Number enrolled across all University affiliated sites as of today's date:** 335**Number enrolled across all sites since last Continuing Review:** -459

- **Describe the progress of the study, observations of the participants studied, and reason(s) for continuing the study:**

Utah has completed accrual. We would like to keep the protocol open for enrollment until NYU completes questionnaire 2, which is anticipated in April 2024.

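### The claimed 80% power at 1,710 patients for an interaction odds ratio of 1.5 cannot be reached (about 55% at best), yet it is the stated reason for enrolling 1,920

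*Combined protocol and SAP*

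**What the plan says.** All places are in the combined protocol and SAP, section 4 (Study Information), item 9, unless noted.

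- **Aim 2 Analysis.** Under Reach, interaction terms will be added to the regression models: "we will examine whether the effects of study arm on uptake of genetic testing is modified by race/ethnicity or rurality".
- **Aim 2 Sample Size.** The equivalence test is sized first: "Sample sizes of 480 in the patient-directed arm and 480 in enhanced standard of care arm", 960 in all. Effect modification is then sized for a logistic regression of a binary outcome on a binary independent variable and a binary confounder, with a two-sided Wald test: "A sample size of 1,710 observations achieves 80% power at a 0.05 significance level to detect the X-Z interaction odds ratio of 1.5". The next sentence is: "We will therefore enroll 1,920 patients in the Aim 2 trial to allow for about 10% attrition".
- **Aim 3 Analysis.** As in Aim 2, "we will examine effect modification by testing for significant interactions between variables in regression models".
- **Aim 3 Sample Size.** The main regression is sized at 1,100: "We estimate a sample size of 1,100 for a multilevel multivariable regression analysis with >90% power". The interaction claim then returns unchanged: "with a sample size of 1,710 observations achieves 80% power at a 0.05 significance level to detect the X-Z interaction odds ratio of 1.5".

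Neither sample-size paragraph gives the baseline uptake, the share of patients in the smaller subgroup, or the main-effect odds ratios behind the 1,710.

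**The concern.** An interaction contrast in a logistic model combines four cell-specific log odds, so its standard error is about twice that of a main effect at the same total size. An interaction odds ratio as modest as 1.5 normally needs several thousand patients, so 80% power at 1,710 looked too good.

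Two things depend on it. Whether the arm effect differs by race/ethnicity or rurality is a named question in Aims 2 and 3, and disparities in access are part of the trial's stated rationale. A reader who believes the test has 80% power will take a non-significant interaction as fair evidence that the two delivery models work alike across groups. If power is 55% or less, the chance of missing an odds ratio of 1.5 is at least 45%, not 20%. Also, the figure is the only power reason given for going from the 960 needed for equivalence to 1,920.

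**Working it through.** **Inputs, all from Aim 2 Sample Size:** N = 1,710; interaction odds ratio 1.5, so ln(1.5) = 0.4055; two-sided α = 0.05 (critical value 1.960); claimed power 80%; binary outcome, arm (X) and modifier (Z). Observations are treated as independent.

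**Is 1,710 a total?** 1,710/0.90 = 1,900, and 1,710/1,920 = 0.891, a loss of 10.9%. That fits the stated attrition of about 10%, so 1,710 is the total across both arms.

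**Variance.** With n patients and outcome probability p in each of the four X–Z cells,

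Var(log interaction OR) = Σ 1/[n p(1−p)].

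Since p(1−p) ≤ 1/4, this is at least 4 Σ(1/n). For four cells summing to N, Σ(1/n) ≥ 16/N. Hence Var ≥ 64/N and SE ≥ 8/√N. The bound does not involve the unstated inputs. Unequal cells, or probabilities away from 0.5, only raise the variance.

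**Plan's figure.** SE ≥ 8/√1,710 = 0.1935; z ≤ 0.4055/0.1935 = 2.096; power ≤ Φ(2.096 − 1.960) = 0.554. The stated 80% is not reproduced. Optimising numerically over cell shares, baseline rate and both main effects, with the interaction fixed at 1.5, gives a best attainable power of 55.3%. Simulating the Wald test at that optimum (400,000 runs) also gives 55.3%.

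**Size needed for 80%.** N ≥ 64 × (1.960 + 0.842)²/0.4055² = 3,056.

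**Ceilings at the sizes in the plan.** The smallest detectable OR at 80% power is at least exp(2.802 × 8/√N).

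| N | Source | Power at OR 1.5, at most | Detectable OR, at least |
|---|---|---|---|
| 960 | equivalence test | 35% | 2.06 |
| 1,100 | Aim 3 regression (binary outcomes) | 39% | 1.97 |
| 1,710 | interaction claim | 55% | 1.72 |
| 1,920 | enrolment target | 60% | 1.67 |

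**Less favourable inputs (assumed, since the plan gives none).** Take 1:1 arms, uptake u in three cells, and odds 1.5 times higher in the fourth. With a 20% subgroup and u = 30%, the cells are 684, 684, 171 and 171, with uptake 0.30, 0.30, 0.30 and 0.391:

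- Var = 2 × 0.00696 + 0.02785 + 0.02455 = 0.0663, so SE = 0.2575.
- z = 0.4055/0.2575 = 1.574; power = Φ(1.574 − 1.960) = 35%.
- 80% would need about 5,400 patients.

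Over subgroup shares of 10–50% and u of 10–50%, power at 1,710 runs from about 13% (10% and 10%) to 55% (50% and 50%).

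**Other readings.**

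- One-sided 0.05: at most 67%, and the text says two-sided.
- A two-sided α of about 0.21 would be needed to reach 80%.
- 1,710 per arm (3,420 in all): up to 84%, but the attrition step rules this reading out.
- A main-effect odds ratio of 1.5: up to 98.7%, but that is a different test.

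**The case against.** The strongest reply accepts the bound and disputes its weight. The trial's hypothesis is equivalence in uptake and adherence; effect modification is subsidiary, the equivalence calculation stands, and the error led to a target above 960, not below it. That is right about scope. It does not make a stated power figure true, and the figure remains the written basis for 1,920.

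Second, 1,920 is also twice 960, and 960 is the approved enrolment at each site, so the target may have another origin. Possibly, but the plan gives no such reason, and its own wording ties 1,920 to the interaction figure.

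Third, the ceilings apply to 1,710 and 1,920, which may not be the numbers analysed. Uptake is followed through health records, of which up to 20,000 may be accessed, so Aim 2 could have more patients. Conversely, the continuing review of 12/15/2023 counts 335 questionnaire completers; the same bound at 335 gives at most 15% power and a detectable odds ratio of at least 3.40 for binary questionnaire outcomes. This point stands. The restated figures should use the number expected to be analysed for each outcome, and 1,100 serves only as an example for Aim 3.

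Finally, the source of 1,710 is unknown. A mislabelled main-effect calculation could have produced it, so retrieving the original software run is a sensible first step. No such explanation makes the sentence correct as written.

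**Conclusion.** The concern holds. For the test the plan describes, power at 1,710 is at most 55.4%, not 80%; 80% needs at least 3,056 analysed patients. The ceiling rests only on the stated model, test, odds ratio and total, plus independent observations. The lower figures, such as 35% at 30% uptake with a 20% subgroup, rest on assumed inputs and are illustrations.

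The error sits in both sample-size paragraphs and concerns the race/ethnicity and rurality analyses of binary outcomes. It leaves 1,920 without a valid stated power basis beyond the 960 for equivalence. It does not touch the equivalence calculation. The statement is wrong as written and must be corrected.

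**What to change.** 1. **Aim 2 Sample Size.** Retrieve the original calculation and replace the sentence with one of this form: *With [u]% uptake and [s]% of patients in the smaller subgroup, 1,710 analysed patients give [x]% power for an interaction odds ratio of 1.5 (about 55% at best under any inputs); the smallest interaction odds ratio detectable with 80% power is [y] (at least 1.72).* If a different number will be analysed for uptake, recompute at that number.
2. **Aim 3 Sample Size.** Give the same statement at the number expected for each binary outcome, keeping questionnaire and health-record outcomes apart. At 1,100 it would read at most 39%, with a detectable odds ratio of at least 1.97.
3. **Enrolment target.** Stop presenting 1,920 as giving 80% power for this interaction. The plan's equivalence calculation needs 960, so an equivalence-based reason for 1,920 would need its own restated calculation.
4. **Interpretation.** Add that subgroup-specific arm differences will be reported with confidence intervals and that a non-significant interaction will not be read as absence of effect modification.

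The work is a short recalculation, new wording in two paragraphs and one interpretation sentence. The real cost is that the stated power falls and 1,920 loses its only stated power basis until another is given. No larger sample is proposed: the continuing review of 12/15/2023 reports that "Utah has completed accrual".

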Patients meeting National Comprehensive Cancer Network guidelines for referral for genetic services will be identified using the screening tool developed and implemented in the EPIC EHR (Study Aim 1). The primary care providers (PCPs) of eligible patients will be notified of their patient's eligibility one week prior to patients being notified of the recommendation for genetic services. Patients will then be referred to participate in standard of care genetic services, with the clinical procedures depending on the study arm to which the clinic was randomized: enhanced standard of care or patient-directed standard of care.

Patients meeting criteria will be notified of the recommendation through the patient portal (i.e. MyChart). Those who do not have MyChart will be notified by mail. Those notifications will be followed by standard scheduling procedures. Patients who do not have MyChart will be asked to sign up for MyChart when they are contacted. Those who were not actively using MyChart will be provided with a refresher on the use of MyChart since this project focuses on using this tool to deliver genetic services more effectively.

Patients who do not have access to the internet or are unwilling or able to use MyChart will be directed to in person genetic counseling services. A waiver of consent will be requested to track the individuals who are not able to participate through MyChart, but they will not be asked to complete study questionnaires.

Study Arms – Clinic Randomized

Enhanced Standard of Care

This arm is referred to as enhanced since clinical decision support (CDS) tools are used to identify patients meeting guidelines rather than relying solely on provider identification of patients. Patients in this arm will have an in-person or telephone pre-test genetic counseling visit. Pre-test counseling includes review of the family history, risk assessment, discussion of the purpose of genetic testing and possible outcomes, implications for insurance coverage, costs, and assessment of psychosocial needs.

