Patients can opt to proceed with genetic testing during this session. Consent for testing will be documented and a sample can be collected at that time or scheduled at another time that is convenient for the patient. All test results are returned by a genetic counselor by phone or in person based on patient preference per clinic protocol. A copy of the results and letter with tailored screening recommendations are returned to the PCP and patient via the patient portal (i.e. MyChart) or via a letter in the mail.

Patient-Directed Standard of Care

Patients in this arm will be offered genetic services through the patient portal (i.e. MyChart). These educational resources will present standard pre-test genetic counseling information as described in the Enhanced Standard of Care Arm. Patients who decide to proceed with genetic testing will be asked to document consent for testing.

Patients who decide to have genetic testing will have a saliva collection kit, instructions, and shipping materials sent to their homes to collect and return a sample to the testing laboratory; this is a service offered by commercial laboratories. Patients will have an opportunity to contact the genetics clinic with any questions or to request an appointment with a genetic counselor at any time.

All results will be reviewed by a genetic counselor. Negative results will be returned along with a letter including screening recommendations tailored based on family history to the patient and PCP via the patient portal. Genetic counselors will return results for pathogenic variants and variants of uncertain significance via phone. A copy of the results and letter with tailored screening recommendations will be provided to the patient and PCP via the patient portal.

All patients will be offered the option to schedule follow-up appointments in the genetics clinics; these contacts and appointments will be tracked.

Standard of Care Genetic Testing

Genetic testing will be performed at Clinical Laboratory Improvement Act (CLIA)-certified, commercial laboratories. Based on standard clinical practice, the choice of laboratory will be based on services provided and patient's insurance and/or financial status. Testing will be billed to insurance. Patients who are uninsured or lack coverage for genetic testing will be assisted in applying for aid through programs offered by the laboratories.

Genetic testing will not be required to participate in the research questionnaires.

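### Comprehension is scored against genetic counselors' notes, whose content and availability may differ by arm, and the plan neither sets a common answer key nor masks the scorer

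*Combined protocol and SAP*

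**What the plan says.** All places are in the combined protocol and SAP, section 4 (Study Information).

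- **Scoring rule (item 9, Aim 3 Analysis).** The sentence opens "For comprehension, concordance between patient responses and information from genetic counselors" and gives the rule as "concordance between patient responses and information from genetic counselors' notes will be scored". No rubric, scorer or masking is given, and nothing says which notes are used or what stands in when there was no conversation.
- **Use of the score (same paragraph).** "We will test bivariate relationships between the outcome variables and study arm", followed by multilevel regression.
- **Enhanced arm (item 6).** "Patients in this arm will have an in-person or telephone pre-test genetic counseling visit". At the other end, "All test results are returned by a genetic counselor by phone or in person based on patient preference per clinic protocol".
- **Patient-directed arm (item 6).** "Patients in this arm will be offered genetic services through the patient portal (i.e. MyChart"). For negatives, "Negative results will be returned along with a letter including screening recommendations tailored based on family history to the patient and PCP", through the portal. A counselor reviews every result and phones when a pathogenic or uncertain variant is found. Patients may ask for a counselor at any time.
- **Who is scored (item 6, Research Procedures).** Comprehension is listed in Questionnaire #1 for those who test, about 4 weeks after results. Questionnaires completed by telephone are recorded so that comprehension can be analyzed.

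**The concern.** A comparison of comprehension needs the same yardstick in both arms. Here the yardstick is a by-product of counselor contact, and counselor contact is the randomized difference. A note of a counseling session or disclosure call may hold more, or different, material than a note made when a counselor reviewed a result and released it by portal. A fuller key could make agreement harder to reach; a thin key could make it easier; a missing note could leave the response unscorable. A note that describes a session or a call may also tell the scorer which arm the patient was in.

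At stake is whether a comprehension difference between arms, or the absence of one, reflects the delivery model or the way answers were marked. A larger sample does not remove that ambiguity.

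**Working it through.** **1. The plan's own Aim 3 figure.** Aim 3 Sample Size states N = 1,100 and power above 90% for an effect size of 0.02, 2 tested variables, 20 covariates and alpha 0.05. Noncentral F: df1 = 2, df2 = 1,100 − 23 = 1,077, λ = 1,100 × 0.02 = 22. Power is 99.1% (99.2% if 0.02 is read as R²). Borrowing the Aim 2 ICC of 0.05 and its 15 patients per clinic, the design effect is 1 + 14 × 0.05 = 1.70, effective N is 1,100 / 1.70 = 647, and power is 90.5%. At 30 per clinic it is 1 + 29 × 0.05 = 2.45, effective N 448, power 76.6%. The stated figure is reproduced without clustering and at 15 per clinic. It does not bear on scoring bias.

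**2. What can generate a counselor note, by arm (item 6).**

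| Stage | Enhanced | Patient-directed |
|---|---|---|
| Pre-test | Counselor visit, in person or by phone | Portal education; counselor on request |
| Negative result | Returned by a counselor | Counselor review, then portal with letter |
| Pathogenic or uncertain variant | Returned by a counselor | Counselor phone call |
| Result and individualized letter to patient | Yes | Yes |

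The arms differ most in the negative-result row. They are close in the row below it, and the last row is common to every tested patient.

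**3. Who could be exposed.** Chiefly patient-directed testers with a negative result who had no counselor contact. The documents give no share of negative results. If it were 60–80% (an assumption), up to that share of the arm's testers would be in this group, fewer to the extent that some asked for a counselor. This counts exposure and does not measure bias.

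**4. From scoring to a spurious gap (illustration).** Let T be true comprehension, equal in both arms, and let s be the chance that a correct answer is scored concordant. The gap is T × (difference in s). For T = 0.60 to 0.80, a 5-point difference in s gives 0.60 × 5 = 3 to 0.80 × 5 = 4 points; a 10-point difference gives 6 to 8.

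**5. What such a gap would do to the test (illustration).** Assume 550 per arm (1,100 split equally), no true difference and a two-sided 5% two-proportion test. The rejection rate is Φ[(d − 1.96·s0)/s1] + Φ[(−d − 1.96·s0)/s1], with s0 the pooled and s1 the unpooled standard error. Example: 70% against 75%. s0 = √(0.725 × 0.275 × 2/550) = 0.0269; s1 = √[(0.70 × 0.30 + 0.75 × 0.25)/550] = 0.0269; (0.05 − 0.0528)/0.0269 = −0.10; rate 0.459. The clustered column divides 550 by 1.70 (patient-directed) and 2.45 (enhanced).

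| Scoring-only gap | Baseline 50% / 70% / 80%, no clustering | Same, with design effects |
|---|---|---|
| 0 points | 5% / 5% / 5% | 5% / 5% / 5% |
| 3 points | 17% / 20% / 25% | 11% / 12% / 14% |
| 5 points | 38% / 46% / 59% | 21% / 25% / 32% |
| 10 points | 92% / 97% / 100% | 64% / 75% / 90% |

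The last continuing review reports 335 people (237 at Utah, 98 at NYU) who completed either questionnaire, so fewer testers would be scored than the 1,100 assumed here. False-positive rates would be lower, but the bias in the estimated difference would be the same.

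**The case against.** The strongest reply is that the notes are never described. The rule refers to information from the notes, which need not mean a record of conversation. Counselors review every patient-directed result, so some record may exist for portal-returned negatives too, though none is promised. If scorers take only the result category and the recommendations, the key is in substance common to both arms. The approved questionnaires listed in the continuing reviews are titled by testing status, with none by arm, so testers in both arms appear to answer the same items; extra detail in a note matters only if an item asks about it. The document also calls itself a summary and points to a full protocol published elsewhere, which may say more.

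Much of this stands, and it rules out three stronger readings that a reader might infer:

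- **That the comparison is not like with like.** The documents show only that it may not be.
- **That the notes reveal the arm.** This is plausible for a note of a session or call, but it is inference.
- **That every patient-directed tester with a negative result is mis-scored.** Some may have asked for a counselor, and a review note may suffice for others.

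What the reply does not supply is a safeguard. Nothing restricts the key to content held for both arms, covers the patient with no conversation, or keeps arm from the scorer. The questionnaire items are not in the documents, so shared items cannot be shown to remove the problem.

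**Conclusion.** The concern holds as a risk that the plan leaves open: the answer key may differ between arms in content or availability, and may disclose arm to the scorer. It is more than missing detail, because the one rule that is stated ties the key to the activity that the arms vary. It is concentrated in patient-directed testers with a negative result and no counselor contact, and is smaller where a counselor phones the result in both arms.

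The size and direction of any bias cannot be known from the documents. The rejection rates above show only how sensitive the comparison would be; they rest on assumed gaps, 550 per arm, 50–80% scored correct, and an ICC and cluster sizes borrowed from Aim 2. Comprehension is one of several Aim 3 responses. The two hypotheses in section 1, item 6 (testing uptake and adherence) are untouched. The change is worth making because a common key already exists for everyone who is scored.

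**What to change.** In Aim 3 Analysis, replace counselors' notes as the reference. In both arms, score the comprehension items against one key taken from the returned result and the letter of individualized screening advice, which item 6 says tested patients in both arms receive. Give the scorer only the study ID, the key and the comprehension responses, with arm, counseling notes and the items on experience of counseling removed. How results reach patients does not change.

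If scoring has already been done, rescore with this key or report it as a sensitivity analysis; at most the 335 completers reported in the last continuing review are involved, apart from any who have responded since.

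The cost is a revised scoring instruction and staff time to prepare the stripped extracts; no new patient contact is needed. There are two other downsides. Points covered only in conversation go unscored. Masking may be incomplete for recorded telephone responses, which should be acknowledged when the result is reported.
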